4.2.5 Secondary endpoints

4.2.5.1 PFS

PFS will be summarized using Kaplan-Meier estimates of the median event time and quartiles together with their 95% CIs, given the anticipated maturity of 60%. The Kaplan-Meier curves will be provided. The no. and proportion of cases of events (e.g. PD, death) and censorings will be summarized.

4.2.5.2 APF12

APF12 will be estimated using the Kaplan-Meier curve. The estimate along with confidence intervals using Greenwood's estimate of standard error and a log-log transformation will be presented.

4.2.5.3 ORR

ORR will be summarized descriptively, and the exact 95% CIs will be provided. Best overall response before a further anti-cancer therapy in the study will be summarized. No. and proportion of patients with each kind of best overall response will be presented.

4.2.5.4 DoR

Kaplan-Meier plot will be produced using the same methods as PFS whenever appropriate. Otherwise, descriptive statistics will be presented.

4.2.5.5 OS

OS will be analysed in the same methods as PFS.

4.2.5.6 OS12

OS12 will be analysed in the same methods as APF12.

4.2.5.7 Incidence of AEs, SAEs, AESIs and AEs leading to treatment discontinuation

Analyses similar to the primary endpoints will be conducted for overall AEs, SAEs, AESIs and AEs leading to discontinuation of study treatment. In addition, the no. and percentage of patients with AEs will be presented by PT.

All above AEs will be listed. Detailed statement of death will be listed.

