1.2 Study design

This will be an open-label, single-arm, multicenter, Phase IIIb study to determine the safety of durvalumab + etoposide and cisplatin or carboplatin as first-line treatment in patients with extensive stage small-cell lung cancer. Patients who fulfil all the inclusion criteria and none of the exclusion criteria will be enrolled and receive treatment with durvalumab + etoposide and either cisplatin or carboplatin (EP) for 4 to 6 cycles. Durvalumab will be administered at a dose of [REDACTED] every 3 weeks (Q3W) with first-line chemotherapy (EP) and will continue to be administered as monotherapy every 4 weeks (Q4W) post-chemotherapy until progressive disease (PD). Prophylactic cranial irradiation (PCI) is allowed at the investigators' discretion as per standard of care (SoC) guidance for extensive stage small-cell lung cancer (ES-SCLC). Patients will attend a safety follow up visit 90 days after last dose of durvalumab. The study flowchart is shown below in Figure 1 Overall study design.

Figure 1 Overall study design

ES-SCLC Extensive-stage small-cell lung cancer; EP etoposide + cisplatin or carboplatin; PD Progressive disease

The schedule of assessments including safety, tolerability, and efficacy using RECIST version 1.1 are detailed in the study assessment schedule in Appendix A.

Tumour assessments using computed tomography (CT)/magnetic resonance imaging (MRI) will be performed at the times specified in the schedule of assessment (Appendix A). RECIST 1.1 measurements as assessed by the Investigator will be used to derive the secondary variables of PFS, APF12, ORR, and DoR. The categorisation of objective tumour response assessment into complete response (CR), partial response (PR), stable disease (SD), progressive disease (PD) or not evaluable (NE) will be based on RECIST 1.1.

Patients will be followed for survival status every 3 months (q3m) following treatment discontinuation, until death, withdrawal of consent or the end of the study. These contacts may be conducted by phone and the survival data collected will be reported in the clinical database.

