An AstraZeneca medically qualified expert after consultation with the Global Patient Safety Physician has reviewed the AEs of interest and identified which MedDRA preferred terms contribute to each AESI. A further review will take place prior to Database lock (DBL) to ensure any further terms not already included are captured within the categories. Specific terms(PT and SOC) will be defined in an external file.

AEs leading to treatment discontinuation including AEs leading to durvalumab permanently discontinuation and AEs leading to EP permanently discontinuation.

The incidence rate of AEs/SAEs/AESIs/AEs leading to treatment discontinuation (%) = No. of patients with at least one AEs/SAEs/AESIs/AEs leading to treatment discontinuation / No. of patients in SS *100, results round to 1 decimal place.

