4.1.6 Data derivation rules

The data derivation rules are describe as follows:

Table 5 Variable derivation rules

Variable (unit)	Definition	Derivation rules
Age (years)	Years from birth date to informed consent	Integer part of $((\text{date of informed consent} - \text{date of birth}) / 365.25)$
Time from first dose of study treatment to the date of disposition event (months)	Months from the date of first dose of study treatment to the start date of disposition event	$(\text{Start date of disposition event} - \text{date of first dose of study treatment} + 1) / 30.4375$, round to 2 decimal place
Time from original diagnosis to informed consent	Months from the date of original diagnosis to the date of informed consent	$(\text{Date of informed consent} - \text{date of original diagnosis}) / 30.4375$, round to 2 decimal place
BMI at each visit (kg/m ²)	Weight over squared height	Weight at each visit (kg) / height at screening (m) ² , round to 2 decimal place
Time from original diagnosis to the first	Months from the date of original diagnosis of SCLC	$(\text{Date of first dose of study treatment} - \text{date of original$

dose of study treatment (months)	to the date of first dose of study treatment	diagnosis of SCLC + 1) / 30.4375, round to 2 decimal place
Time from the latest assessment to the first dose of study treatment (months)	Months from the date of latest assessment of SCLC to the date of first dose of study treatment	(Date of first dose of study treatment – date of latest assessment of SCLC + 1) / 30.4375, round to 2 decimal place
Time to first AE (days)	Days from the date of first dose of study treatment to the date of first AE occurrence or censoring	Date of first AE or censoring – date of first dose of study treatment +1
Duration of AE (days)	Days from the AE start date to the AE stop date or date of DCO. The date used should not be imputed.	AE stop date or date of DCO – AE start date +1

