4.2.4 Primary endpoints

Adverse events, which start after first dose of study drug up to 90 days after the last dose of durvalumab treatment or the date of initiation of the first subsequent therapy, whichever occurs first, will be analysed in summary table. Other AEs recorded in the study will only be listed. This rule applies to all analysis of AE.

Frequency of AEs of CTCAE grade ≥ 3 , no. and percentage of patients with AEs of CTCAE grade ≥ 3 will be presented. These AEs will also be summarized by System Organ Class (SOC) and preferred term (PT). The exact 95% CIs around the incidence estimates will also be reported.

Time to event endpoints will be analysed using Kaplan-Meier method to estimate the median event time to the first AE of CTCAE grade 3 or higher. If a patient has no AE of CTCAE grade 3 or higher, the time to event will be censored at the date of DCO, death, 90 days after

the last dose of durvalumab treatment or the date of initiation of the first subsequent therapy, whichever occurs first. K-M curve will be presented.

Similar analyses will be conducted for imAEs.

An imAE is defined as an AESI that is associated with drug exposure and is consistent with an immune-mediated mechanism of action and where there is no clear alternate etiology. In general, imAEs will include AESIs that are managed using steroids, immunosuppressants and/or hormone replacement therapy.

The identification of imAEs will be made following the AstraZeneca imAE characterization charter.

1. The selection of preferred term,
2. Programmatic identification of those potential imAEs requiring medication such as steroids, immunosuppressants and/or hormone replacement therapy

All imAEs which are identified by the investigator (as recorded in CRF Adverse Events (AE)) will undergo a review by medical monitor. In addition, imAEs will be checked programmatically as described in the imAE charter on the clinical database to ensure the recording of imAEs are complete and unambiguous. If any discrepancies found, those will be resolved as an on-going basis and before DBL.

All above AEs will be listed.

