5 INTERIM ANALYSES

There will be no formal interim analysis in this study.

As the safety of durvalumab + EP has not been previously established in ES-SCLC patients with PS2, a safety review committee (SRC) will be established to review the safety and tolerability data of the combination of durvalumab+EP in this subset of patients at an early stage of enrolment. SRC will include AZ local study team member such as study physician, PV physician, PM and local medical affairs Lead, and also global clinical lead, global patient safety physician and GMAL.

The SRC will meet after the first 20 patients with PS2 have either had the opportunity to complete the combination of durvalumab + chemotherapy (maximum of 6 cycles) or have discontinued treatment with durvalumab due to an AE or disease progression, whichever occurs first.

After review of the data in patients with PS2, and patients with PS0-1, the SRC will make a recommendation on whether the study should continue recruitment of patients with PS2 as planned, or hold recruitment of this patient population, or amend the study design. In the event that the SRC recommends a change to the study, this will be communicated to all sites.

The primary analysis of the study will be conducted 6 months after LSI, at which time secondary endpoints will also be assessed (maturity for PFS is anticipated to be approximately 60%).

Additionally, final analysis will be performed at the end of the study when all patients have completed follow-up for safety or sufficient maturity for the secondary efficacy objectives has been reached.

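### The Kaplan-Meier curve carried over to AEs leading to discontinuation keeps patients in the risk set after the event has become impossible, so it estimates neither natural quantity

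*SAP*

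**What the plan says.** Section 4.2.5.7 of the SAP covers four groups of events in one sentence: "Analyses similar to the primary endpoints will be conducted for overall AEs, SAEs, AESIs and AEs leading to discontinuation of study treatment". The primary-endpoint analyses in Section 4.2.4 are counts, percentages with exact 95% CIs, and a Kaplan-Meier analysis of the time to the first AE of at least grade 3, with a median and a curve. A patient without the event is censored at the earliest of four dates. Data cut-off and death are two of them. The other two are in the part of the rule that reads "the last dose of durvalumab treatment or the date of initiation of the first subsequent therapy, whichever occurs first. K-M curve will be presented"; the count there is 90 days.

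Table 5 in Section 4.1.6 has one general rule for time to first AE, "Date of first AE or censoring – date of first dose of study treatment +1", with no version specific to discontinuation. Section 3.2.9 defines the event: "AEs leading to treatment discontinuation including AEs leading to durvalumab permanently discontinuation and AEs leading to EP permanently discontinuation". The same section defines the incidence as patients with at least one such event divided by all patients in the safety set.

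No section gives a different risk period for AEs leading to discontinuation. Stopping treatment for a reason other than an AE is neither a censoring event nor a competing event.

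**The concern.** For grade 3 or higher AEs, imAEs, SAEs and AESIs, the 90 days after the last durvalumab dose are real time at risk. For AEs leading to discontinuation they are not, once durvalumab and EP have both been permanently stopped: there is nothing left to discontinue. A patient who stops everything for progression, and who neither dies nor starts another therapy, is still counted as event-free and at risk until the 90 days run out. This happens even when AE follow-up is complete, so it is a separate matter from loss of observation.

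Many patients are involved. Section 1.2 has durvalumab continuing until progression, and Section 5 states that "maturity for PFS is anticipated to be approximately 60"% at the primary analysis. With about 300 patients that is 0.60 × 300 = 180 progressions or deaths.

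At stake is how the curve is read. A reader will take it either as the risk of an AE discontinuation while on treatment, or as the proportion of patients who stop for an AE. It is neither.

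**Working it through.** The SAP gives no figure for this analysis. Its only design calculation, Table 1, reproduces (Clopper-Pearson half-width 5.69% for n = 300 at 60%, stated as 5.7%) and is not at issue. What follows is an illustration. The rates are assumptions, not SAP values.

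**Quantities compared at 12 months.** Let h be the monthly hazard of an AE discontinuation on treatment and g the hazard of stopping for another reason.

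- On-treatment risk (censor at stopping): 1 − exp(−12h)
- Cumulative incidence (other-reason stopping competes): h/(h+g) × [1 − exp(−12(h+g))]
- SAP rule: 1 − Kaplan-Meier, with each other-reason stopper kept at risk for min(90 days, death, subsequent therapy)

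**Case A.** h = 0.025; median time to other-reason stopping 5 months, so g = ln 2/5 = 0.1386; median survival after stopping 6 months; 30–70% start subsequent therapy, on average 1 month after stopping.

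- On-treatment risk: 1 − exp(−0.30) = 25.9%
- Cumulative incidence: 0.025/0.1636 × [1 − exp(−1.963)] = 0.1528 × 0.860 = 13.1%
- SAP rule, by simulation of 400,000 patients: 20.7–22.1%

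Over h = 1.5–2.5% per month and medians of 5–6 months, the tail adds 1.4–2.0 months per other-reason stopper. The ratio of true to counted risk time is 0.78–0.87.

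**Case B, a separate set of assumptions.** Median time to stopping for any reason 6 months (total hazard ln 2/6 = 0.1155), 10% of stops due to an AE (h = 0.01155), data cut-off 6–24 months after first dose.

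| 12-month estimate | Result |
|---|---|
| Censoring at treatment stop | 13.0% |
| SAP rule, shorter tail (mean 1.5 months, capped at 90 days) | 11.6% |
| SAP rule, full 90 days | 10.1% |
| Cumulative incidence, 0.10 × (1 − 2^(−12/6)) | 7.5% |

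Hand check of the full-tail row. The tail is 90/30.4375 = 2.96 months. After that time the share of the risk set that has already stopped is 0.9(e^0.3416 − 1)/[1 + 0.9(e^0.3416 − 1)] = 0.3665/1.3665 = 27%. The Kaplan-Meier hazard is h times the share still on treatment, which is 0.73 after 2.96 months and averages about 0.86 before. So the cumulative hazard is 0.01155 × (0.86 × 2.96 + 0.73 × 9.04) = 0.106, and 1 − exp(−0.106) = 10.0%, in line with the simulated 10.1%.

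Across medians of 4, 6 and 9 months and AE shares of 5%, 10% and 20%, 8–39% of the risk set at 3 to 9 months could no longer have the event. The SAP-rule estimate lay between the other two at 12 months in every scenario, and its median was never reached. The crude n/N does not use the risk set and does not change.

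**The case against.** Several points on the other side stand.

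- **The endpoint itself is untouched.** A reader might infer that the secondary tolerability endpoint is biased. It is not: Section 3.2.9 defines it as a crude proportion of the safety set, and the exact CI around it remains valid. Only the added curve and median are affected.
- **The carry-over is inferred.** Section 4.2.5.7 says similar, under a heading about incidence, and does not name Kaplan-Meier. But no alternative is given and Table 5 has a general time-to-first-AE rule, so carry-over is the natural reading. If it is not intended, the SAP should say so.
- **No 12-month AE estimate is planned.** Section 4.2.4 asks for a median and a curve. The 12-month values above are readings off that curve, and no person-time rate will be reported.
- **Not every patient carries 90 dead days.** The clock starts at the last durvalumab dose, not at the decision to stop. An AE before the next due dose can still lead to discontinuation. With an assumed 28-day lag the dead time is at most 90 − 28 = 62 days, and the 14–22% shortfall in the event rate over counted time becomes about 11–17%. Death, data cut-off or subsequent therapy shortens it further. A patient off durvalumab but still on EP remains at risk.
- **PS comparisons.** It is tempting to argue that a faster-progressing PS cohort would look better tolerated and that a competing-risk curve would cure this. Neither part carries far. Section 4.2.8 requires 20 events per subgroup level for time-to-event analyses; at 13% incidence that takes about 20/0.13 = 154 patients, so small PS cohorts would get no curve. And cumulative incidence depends more on speed of stopping, not less. At h = 0.025 and medians of 3 and 6 months it is 0.025/0.2560 × [1 − exp(−3.073)] = 9.3% and 0.025/0.1405 × [1 − exp(−1.686)] = 14.5%. The SAP-rule curve gives about 17.6% and 21.5% (30% starting subsequent therapy).

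**Conclusion.** The concern holds in limited form. As written, Section 4.2.5.7 most naturally prescribes a curve whose risk set includes patients who can no longer have the event. The result falls between two meaningful quantities and estimates neither. That follows from the definitions and needs no assumed rates; the size does. In Case A the gap at 12 months is about 4–5 percentage points below the on-treatment risk (25.9% against 20.7–22.1%) and about 8–9 points above the cumulative incidence (13.1%). A lag between last dose and stopping decision moves the curve nearer to the on-treatment risk.

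The importance is minor to moderate. The study is descriptive, without hypothesis tests on the primary endpoints, and the proportion stopping for an AE is already reported correctly as a crude incidence.

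**What to change.** In Section 4.2.5.7, keep the crude incidence with its exact CI, and for AEs leading to discontinuation replace the carried-over Kaplan-Meier curve and median. Suggested content: time to first AE leading to discontinuation is shown as an Aalen-Johansen cumulative incidence curve; permanent discontinuation of the last remaining study treatment for a non-AE reason (disposition date) and death are competing events; the 90-day extension does not apply.

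Simply censoring at treatment stop is not a substitute if the curve is meant to show how many patients stop for an AE: in Case B it gives 13.0% where the cumulative incidence is 7.5%.

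Add one sentence saying that cumulative incidence depends on how long patients stay on treatment, so differences between PS cohorts should not be read as differences in on-treatment tolerability. Alternatively, state that no time-to-event analysis is done for this endpoint.

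The cost is one or two sentences and a small programming change. Sections 4.1.6 and 4.2.1 already plan to use disposition events and their dates.

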4.2.6 Other safety variables

4.2.6.1 Adverse Events

The following AE summaries will be summarized similar to the primary endpoints:

- All AEs causally related to any study treatment
- All AEs by CTCAE grade
- Any CTCAE grade ≥ 3 causally related to any study treatment
- All SAEs causally related to any study treatment
- All AESIs causally related to any study treatment
- AEs leading to discontinuation of any study treatment, causally related to any study treatment
- AEs that resulted in death
- AEs that resulted in death causally related to any study treatment
- Other significant AEs

AE, AE with CTCAE grade ≥ 3 , AESI and imAE will be summarized by SOC, PT and most severe outcome. The severity of outcome is Fatal > Not Recovered/Not Resolved > Recovered/Resolved with Sequelae > Recovering/Resolving > Recovered/Resolved.

Most common AEs ($\geq 2\%$), most common AEs of CTCAE grade 3 or 4, causally related AEs, causally related AEs of CTCAE grade 3 or 4, AEs leading to interruption of durvalumab/EP/study treatment, SAEs, SAEs causally related to study treatment will also be summarized for PT and maximum CTCAE grade.

A summary of deaths will be provided with the following information:

- Total number of deaths (regardless of date and reason of deaths)
- Death related to disease under investigation only, as determined by the investigator
- Deaths related to disease under investigation, as determined by the investigator, and with an AE with outcome of death (with further subcategories for AEs with onset/worsening date prior to 90 days after the last dose of study treatment and initiation of subsequent anticancer therapy)
- AEs with outcome of death only (with further subcategories for AEs with onset/worsening date prior to 90 days after the last dose of study treatment and initiation of subsequent anticancer therapy)
- Other deaths

A list of all deaths will also be produced.

Any AE with a relatedness to study treatment of possible or probable will be considered to be causally related to study treatment for purposes of the data summaries. Relatedness should be assigned by the investigator to each study treatment individually on the eCRF. When the relatedness of an AE is missing on the eCRF, all efforts will be taken to ensure that the Investigator assigns his/her assessment of relatedness prior to database lock.

If relatedness of an AE is missing at the DBL, the AE will be considered as related to study treatment and related to durvalumab.

4.2.6.2 Exposure

The exposure for durvalumab and each kind of drug of EP will be summarized respectively.

- intended exposure for durvalumab
- actual exposure for durvalumab
- total number of cycles of each molecule received
- number of patients receiving 1, 2, 3, 4, 5, 6, 7, 8, 9, 10, 11, 12, >12 cycles of durvalumab
- number of patients receiving 1, 2, 3, 4, 5, 6, >6 cycles of each drug of EP
- number of, and reasons for, dose delays and interruptions

Additionally, for durvalumab, relative dose intensity will also be summarized.

Dose reductions are not permitted per the CSP for durvalumab and the actual exposure calculation makes no adjustment for any dose reductions that may have occurred.

All these variables will be listed. Overdose report will also be listed.

4.2.6.3 Lab tests

Baseline and post-baseline hematology, clinical chemistry and urinalysis results will be summarized descriptively by visit according to the general principles. For continuous laboratory assessments, absolute value and change from baseline will be summarized using descriptive statistics at each scheduled assessment time. These data summaries will be

provided in international system (SI) of units whenever applicable. The frequency and percentage for each clinical evaluation category (e.g., 'normal' and 'abnormal with/without clinical significance', 'Unchecked') will be summarized by visit. Shift table will be provided to show the change in CTC (V 5.0) grades between baseline and the worst post-baseline case if applicable. For the tests in clinical chemistry without CTC grade, shift table will be provided to show the change from baseline to maximum and minimum value during treatment respectively. For the tests in urinalysis, shift table will be provided to show the change from baseline to the worst value on treatment. Only when there is no post-baseline CTC grades or values, the worst post-baseline/ maximum value/ minimum value of lab test will be considered as unchecked in shift table. For the lab tests in clinical chemistry which have no CTC grades, normal range (low, normal, and high) will be used to evaluate the maximum or minimum value.

Listings will be provided for those whose results are normal at baseline and abnormal in post-baseline evaluations, or abnormal both at baseline and in post-baseline evaluations.

